4.4 Study design

KARE has two interventions (drug therapy and psychological therapy), each with two possible forms, resulting in a two by two factorial intervention design, with a total of four possible interventions (Section 4.1).

The drug intervention will be administered by the site anaesthetist, who will be blinded to drug allocation and psychotherapy allocation. Psychotherapy/psychoeducation will be administered by the trial psychologists at each site who will be blinded to the drug allocation. Participants will also be blinded to drug allocation. Participant outcome data will be collected by site investigators who are blinded to drug allocation. The trial statistician will be blinded to both drug allocation and psychotherapy allocation throughout the trial.

Participants will be randomised to the trial after eligibility has been confirmed via prescreening and screening, and after having provided informed consent. The SCRAM-X ankle monitor (measuring alcohol levels in sweat) will be attached at screening. Treatment will commence as soon as possible after randomisation, and continue for a period of 3 weeks (one infusion session and two sessions of psychological therapy/psychoeducation per week). Follow-up data will be collected at 3 and 6 months after baseline. The last follow-up visit is scheduled for 24 weeks post baseline.

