## 7.2 Randomisation procedures

A blocked design for randomisation will be used to allocate patients using a 1:1:1:1 ratio for the 4 respective groups. Randomisation will be performed by a specialist company ([www.sealedenvelope.com](http://www.sealedenvelope.com)) who will hold the randomisation list and provide 24/7 internet access for unblinding services. Early drop-outs (during screening and the baseline week up until randomisation) will be replaced. Once patients have been randomised at week 0 they will not be replaced regardless of compliance or dropout status and will be analysed as part of the intention to treat analysis. After randomisation, the site research team will be given a unique trial randomisation code via email from [sealedenvelope.com](http://sealedenvelope.com). This code corresponds to an envelope at the site which contains the treatment allocation. These envelopes will be provided by the trial statistician at the start of the trial and are kept in a secure location by allocated partially unblinded staff. The trial statistician will be provided the treatment allocation codes prior to the start of the trial to prepare the envelopes. Separate envelopes will be provided for the delegated staff preparing the IMP (containing the IMP treatment allocation) and the psychology staff (containing the psychological treatment allocation). To protect the blind, pharmacy or delegated unblinded staff preparing the IMP at site will be notified separately via email of the randomisation code. An additional email is sent to the psychology team at site who can refer to the correct envelope to determine the psychological treatment allocation. Randomisation details of patients will be entered on a trial Subject Log and will follow the instructions set out in a Standard Operating Procedure (SOP) on randomisation. Data review will take place when half the target samples have been randomised. Upon randomisation, patients will be given a study specific patient card which will have study title, IMP details, patient ID and contact details of the out of hours contact in cases of emergency.

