### **13.3.2 Primary outcome analysis**

There are two primary outcomes: (i) proportion relapsed (recommenced using alcohol) at 6-month follow-up; and (ii) percentage of days abstinent at 6-month follow-up (the denominator being 175 days). The proportion of relapsed participants at 6-month follow-up will be reported as a percentage for each arm, as well as for the ketamine arms combined and

the psychotherapy arms combined. Although no formal power calculations for a between-group analysis have been performed, the proportion of relapsed participants at 6-month follow-up will be expressed as a relative risk (RR) with a 95% confidence interval for the following comparisons: (i) all ketamine participants versus all non-ketamine participants; (ii) ketamine + psychotherapy participants versus ketamine + non-psychotherapy participants; and (iii) ketamine + psychotherapy participants vs. placebo + no psychotherapy participants. These analyses are purely exploratory and should be viewed with caution both in the light of lack of power and multiple testing. Percentage of days abstinent at 6-month follow-up will be reported descriptively in the same way by arm and combination of arms; additionally, the between-group mean differences and 95% confidence intervals will be reported for the comparisons set out above; again, these analyses should be regarded as exploratory. The primary analysis will be an intention-to-treat (ITT) complete case analysis including all randomised participants. A secondary analysis will be conducted including only those participants deemed to have completed to a sufficient degree their allocated interventions, that is, a per protocol analysis. All analyses will be performed by a statistician who is blinded to the treatment allocations and will be performed using Stata v.13.

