4.3 Randomisation level

Randomisation will be performed by an independent organisation, Sealed Envelope, that specialises in randomisation and online databases for clinical trials (<https://www.sealedenvelope.com/>). Participants are randomised individually. To aim for balance across the four treatment combinations, a block randomisation will be performed (block sizes are known only to the trial statistician and the designated staff at Sealed Envelope). Randomisation will be performed separately for each site. A list of randomisation allocation codes will be generated in advance by Sealed Envelope, with each code indicating the drug allocation (ketamine or placebo) and the psychotherapy intervention (psychotherapy or psychoeducation). These codes will be sent to the trial statistician, who will generate two envelopes for each participant, one indicating the drug allocation and the other indicating the psychotherapy intervention. These envelopes will be securely delivered to trial staff at each site. The trial unblinded research nurse will receive the drug allocation envelopes for the Devon site, and the hospital pharmacist at UCLH. The trial psychologists at each site will receive the psychotherapy allocation envelopes for the Devon and London sites. When recruited by trial researchers, the participant's data will be entered to the online eCRF database. The participant will be allocated a trial ID number. The randomisation will be performed using the online eCRF database by the trial anaesthetist at each site. This trial ID number will be linked to the next available randomisation allocation code, and this information will be sent via email to the relevant member of the trial team so that they can open the participant's envelope to discover their randomised allocation.

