4.5 Purpose of the analyses

The purposes of the analyses are as follows:

- (i) to provide baseline descriptive data by trial arm;
- (ii) to assess the feasibility of data collection;
- (iii) to assess loss to follow-up at 3 and 6 months;

- (iv) to assess the proportion of missing data at 6 months;
- (v) to provide descriptive outcome data by trial arm (ketamine vs placebo, psychotherapy vs psychoeducation, and all four arms individually) at 6 months;
- (vi) to provide relative risks (with 95% confidence intervals) for relapse of alcohol consumption comparing (a) ketamine vs placebo; (b) ketamine plus psychotherapy vs ketamine plus psychoeducation; (c) ketamine plus psychotherapy vs placebo plus psychoeducation;
- (vii) to provide mean difference (with 95% confidence intervals) for percentage of days abstinent at 6-month follow-up for the same combinations by arm as for (vi); and
- (viii) to descriptively report adverse events.

All inferential analyses are to be regarded as exploratory and viewed with caution due to lack of statistical power and multiple testing. For the primary outcomes, the primary analyses will be performed on an intention to treat (ITT) basis using complete case data only (see Section 6.5 for approaches to missing primary outcome data). As a sensitivity analysis, the inferential analyses for the primary outcomes only (vi and vii above) will be performed using only those participants deemed to have completed their allocated interventions to a specified degree (per protocol analysis). For the participants who receive ketamine, a per protocol treatment will be defined as receiving three or more infusions. No specification of a minimum treatment has been defined for psychotherapy/psychoeducation. Hence, all participants who receive placebo drug therapy will be considered as having been treated per protocol. For the secondary outcomes, only an ITT analysis using complete case data will be performed. All analyses will be performed by a statistician who is blinded to treatment allocation. All analyses will be performed using Stata v14.

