5.3 Derived variables

The only derived variables will be the binary relapse variable and the number/percentage of days abstinent, to be derived from timeline follow-back data. Further details are to be confirmed.

6 General analysis considerations

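### The SAP calls the trial statistician blind to both allocations throughout, yet that person receives the full list of allocation codes, so a blinded analysis is not provided for as written

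*SAP*

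**What the plan says.** On blinding, SAP 4.4 is explicit: "The trial statistician will be blinded to both drug allocation and psychotherapy allocation throughout the trial". Protocol 13.3.2 makes the matching claim for the analysis: "All analyses will be performed by a statistician who is blinded to the treatment allocations". SAP 4.5 repeats it in nearly the same terms.

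On who holds the allocations, SAP 4.3 explains that every code shows both the drug and the psychological intervention, and continues: "These codes will be sent to the trial statistician, who will generate two envelopes for each participant". It also says that "block sizes are known only to the trial statistician and the designated staff at Sealed Envelope". Protocol 7.2 agrees and gives the timing: "The trial statistician will be provided the treatment allocation codes prior to the start of the trial to prepare the envelopes".

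On the per-protocol set, SAP 4.5 says: "For the participants who receive ketamine, a per protocol treatment will be defined as receiving three or more infusions". Everyone on placebo counts as treated per protocol, whatever they received.

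**The concern.** A person who writes each allocation into an envelope is not blind to the list of allocations. The two statements stand in adjacent sections of the SAP and concern the same role.

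This matters because some analytic choices are still open. SAP 5.3 says of relapse and the abstinent-days variables, which include both primary outcomes: "Further details are to be confirmed". SAP 6.5 plans multiple imputation for the primary outcomes but gives no model. Blinding the analyst is meant to protect decisions of this kind. If the report repeats the plan's wording, readers will credit the trial with a safeguard that its own procedure does not deliver.

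**Working it through.** No figure in the plan is in dispute. The check sets the sections side by side and adds two small calculations.

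**1. Is the list-holder the analyst?** SAP 4.3 and protocol 7.2 name the trial statistician as recipient of the codes. Protocol 11.3 gives data analysis to the trial statistician, and protocol 13 makes that role answerable for the statistics from planning to publication. SAP 4.5 and protocol 13.3.2 refer only to an unnamed blinded statistician. Neither document describes a second one.

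**2. Can codes be tied to participants?** The list pairs codes with treatments. Under SAP 4.3 each trial ID takes the next unused code, separately by site. Protocol 11.3 lets the trial statistician download the eCRF data. Given the order of randomisation within a site, or the code itself, the list can be matched to people. The documents do not say whether the download contains either item. The only step described for keeping allocation from the statistician is in protocol 13.5, which limits the 3-month attrition look to aggregate data. Nothing similar covers the final analysis.

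**3. Can the per-protocol analysis be run blind?** The rule differs by drug, so whoever applies it must know the drug. Suppose someone else supplied a masked flag. Placebo has no exclusions by definition, so one exclusion identifies a ketamine group. Let p be the share of ketamine participants with fewer than three infusions. The documents give no value, so p is an assumption. With n ketamine participants, treated as independent,

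P(at least one exclusion) = 1 − (1 − p)^n.

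The sample size is 24 per combination, so n = 48 for both ketamine arms together and n = 24 for one arm.

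| Assumed p | n = 48 | n = 24 |
|---|---|---|
| 2% | 62% | 38% |
| 5% | 91% | 71% |
| 10% | 99.4% | 92% |
| 20% | over 99.99% | 99.5% |

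For example, 1 − 0.95^48 = 0.915. The n = 24 column also describes the pooled ketamine group if half are lost, as the sample-size section allows, with p then taken among those followed up. Protocol 9.12 expects such cases: participants who miss two consecutive infusions stop treatment but are still invited to both follow-up visits.

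**4. Would masked arm labels be enough for ITT?** Three contrasts are planned: both ketamine arms against both placebo arms; ketamine + psychotherapy against ketamine + psychoeducation; and ketamine + psychotherapy against placebo + psychoeducation. The arm that appears in both single-arm contrasts must be ketamine + psychotherapy. Its partner in the pooled contrast is ketamine + psychoeducation, its other comparator is placebo + psychoeducation, and the remaining arm is placebo + psychotherapy. Of the 4! = 24 ways to relabel the arms, only the identity leaves the three contrasts unchanged. An analyst who knows the SAP and is told which coded arms to compare can therefore name all four.

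**The case against.** The strongest defence is that a list of codes is not a list of patients. At the start no participant is attached to any code, and the randomisation emails go to site staff, not to the statistician. A reader might infer that all 96 allocations are known to the analyst from day one and that the safeguard is absent for every participant. The documents do not support that: they show allocations that can be reconstructed, not allocations already known.

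A second defence is that the analysis sections speak of a blinded statistician without saying it is the trial statistician. So it goes too far to conclude that no blinded analysis could exist. What stands is that none is provided for as written. Even a separate analyst would leave SAP 4.4 wrong, because it names the trial statistician.

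Third, the per-protocol point is limited. It touches one sensitivity analysis (SAP Table 5), it needs at least one ketamine exclusion, and SAP 4.5 does not say who derives the flag.

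Fourth, the open decisions are fewer than they may look. The drink thresholds, the meaning of abstinence and the data source are fixed in SAP 5.2, and protocol 13.3.2 gives a 175-day denominator. The undecided item-missingness limits in SAP 6.5 concern questionnaires, so they do not reach primary outcomes taken from timeline follow-back. Imputation is additional to the complete-case primary analysis.

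Finally, all inference is labelled exploratory and no p-values are planned. That lowers the stakes but does not make the blinding statement accurate.

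**Conclusion.** The contradiction between SAP 4.3 with protocol 7.2 and SAP 4.4 is direct. As written, the trial statistician holds the means to identify allocations and is also the analyst, so the blinded analysis claimed in SAP 4.5 and protocol 13.3.2 is not provided for. Separately, the per-protocol analysis cannot be run blind once any ketamine participant has had fewer than three infusions. That is likely even at low assumed rates: 62% at 2% and 91% at 5%, among 48.

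The conclusion rests on two readings: that no second analyst exists beyond those described, and that the downloaded data would allow participants to be matched to codes. No bias is shown, and its size cannot be computed from the documents. The blinding of participants, anaesthetists, psychologists (to drug) and outcome collectors (to drug) is unaffected. The point should be corrected, but it does not undermine the trial.

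**What to change.** If envelopes have not been issued, have the randomisation provider, or an existing unblinded person who does no analysis, prepare and release them, so that the analyst never holds the list. The provider already holds it and already notifies the drug-preparation staff and the psychology team separately (protocol 7.2).

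If envelopes are already out, do one of two things:
- assign the analysis to a statistician without access to the list, and say so; or
- correct SAP 4.4, SAP 4.5 and protocol 13.3.2 to state that the analyst is not blinded.

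In every case:
- before outcome data are linked to arm, sign off the remaining derivation details for relapse and percentage days abstinent, the imputation model and the analysis code;
- run the ITT analysis first;
- report the per-protocol analysis as unblinded.

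Masked arm labels alone are not enough, for the reasons in steps 3 and 4 of the working.

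The cost is mainly wording or a change in who handles the list. A separate analyst would need some statistician time. The downside is a less favourable statement about blinding in the report.

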4.5 Purpose of the analyses

The purposes of the analyses are as follows:

- (i) to provide baseline descriptive data by trial arm;
- (ii) to assess the feasibility of data collection;
- (iii) to assess loss to follow-up at 3 and 6 months;

- (iv) to assess the proportion of missing data at 6 months;
- (v) to provide descriptive outcome data by trial arm (ketamine vs placebo, psychotherapy vs psychoeducation, and all four arms individually) at 6 months;
- (vi) to provide relative risks (with 95% confidence intervals) for relapse of alcohol consumption comparing (a) ketamine vs placebo; (b) ketamine plus psychotherapy vs ketamine plus psychoeducation; (c) ketamine plus psychotherapy vs placebo plus psychoeducation;
- (vii) to provide mean difference (with 95% confidence intervals) for percentage of days abstinent at 6-month follow-up for the same combinations by arm as for (vi); and
- (viii) to descriptively report adverse events.

All inferential analyses are to be regarded as exploratory and viewed with caution due to lack of statistical power and multiple testing. For the primary outcomes, the primary analyses will be performed on an intention to treat (ITT) basis using complete case data only (see Section 6.5 for approaches to missing primary outcome data). As a sensitivity analysis, the inferential analyses for the primary outcomes only (vi and vii above) will be performed using only those participants deemed to have completed their allocated interventions to a specified degree (per protocol analysis). For the participants who receive ketamine, a per protocol treatment will be defined as receiving three or more infusions. No specification of a minimum treatment has been defined for psychotherapy/psychoeducation. Hence, all participants who receive placebo drug therapy will be considered as having been treated per protocol. For the secondary outcomes, only an ITT analysis using complete case data will be performed. All analyses will be performed by a statistician who is blinded to treatment allocation. All analyses will be performed using Stata v14.

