Breathalyser tests will be used at each visit for the following reasons:

- Screening & re-screening – To assess eligibility
- Baseline visit (1st infusion) – To assess eligibility/ensure safety of IMP administration/ensure patient is able to complete cognitive tasks and questionnaires, as well as engage with therapy/education
- Visit 3, 5, 7 & 8 – To ensure patient is able to complete cognitive tasks and questionnaires, as well as engage with therapy/education
- Visit 4 & 6 (2nd & 3rd infusion) – To ensure safety of IMP administration/ensure patient is able to complete cognitive tasks and questionnaires, as well as engage with therapy/education
- Visit 9 & 10 - To ensure patient is able to complete cognitive tasks and questionnaires

Once randomised, if a patient attends for any visit and does not blow 0 on the breathalyser the visit will be terminated (either for the primary purpose of safety on infusion visits or of data integrity on non-infusion visits) and the patient invited to re-attend to complete the visit within the allocated visit window.

Concomitant Medication: All prescription medication, over-the-counter medication, vitamins, and/or herbal supplements will be recorded on case report forms (CRFs).

Vital Signs: Resting pulse, pulse oximetry and blood pressure (BP) measurements will be measured at each visit phase for safety monitoring. Vital signs will be continuously monitored throughout the infusion until the participant has recovered. This monitoring will be recorded on a standard

observation chart, stored as source data. The eCRF will record 3 sets of readings, one prior to the infusion, another after the infusion terminates, and then finally after the participants recovery.

Physical Examination: Height, weight and oral/tympanic temperature will be recorded.

At screening a physician will perform a physical examination of the cardiovascular, respiratory, GI and neurological system to a level of detail that would be expected for a patient due to receive anaesthesia.

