## **8 Name and description of all drugs used in the trial**

### **8.1 Treatment of subjects**

Investigational product/treatment

Participants will receive the following:

1. 3 x weekly infusions of IV ketamine hydrochloride (Ketalar®) at a dose of 0.8mg/kg over 40 mins, or
2. 3 x weekly infusion of placebo (50ml Saline 0.9%) over 40 mins.
3. Ketamine is packaged as: Ketalar® glass vial with rubber closure and aluminium flip-off cap containing. Exipients with known effects: Each 1 ml contains 2.6 mg of sodium. The total amount to be delivered will be calculated on the basis of the patient's weight (0.8 mg/kg). Site pharmacy will order ketamine and dispense per patient, added to saline (0.9%) to make up to 50ml solution in syringes for the infusion pump to infuse intravenously. Doses will be administered using a computer controlled infusion pump.

Placebo will be 50 ml saline (NaCl) 0.9% in syringes for the infusion pump.

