4.7 Study populations

Inclusion and exclusion criteria for participants are set out in the Protocol, Final Version 12, 20.01.2020 Section 5.

The primary analyses will be performed using the ITT population (participants analysed according to their randomised allocations). Further sensitivity analyses will be performed using the per protocol population (defined in Section 4.5). All analyses will be performed using complete case data only. Participants found to be ineligible after randomisation will be excluded from all analyses.

5. Study objectives and endpoints

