Table 5 Relapse of alcohol use and percentage of days abstinent at 6-month follow-up: per protocol^a population using complete case data.

Outcome	Ketamine (n=)	Placebo (n=)	PT (n=)	PE (n=)	Ketamine + PT (n)	Ketamine + PE (n)	Placebo + PT (n)	Placebo + PE (n)	Ketamine vs placebo RR (95% CI)	Ketamine + PT vs Ketamine + PE RR (95% CI)	Ketamine + PT vs placebo +PE RR (95% CI)
Relapse; n (%) Timeline follow back											
									Ketamine vs placebo mean difference (95% CI)	Ketamine + PT vs Ketamine + PE mean difference (95% CI)	Ketamine + PT vs placebo +PE mean difference (95% CI)
Percentage days abstinent; mean (SD); median [IQR] Timeline follow back											

^aPer protocol population defined as receiving at least three ketamine infusions. No definition of per protocol for placebo, psychotherapy, or psychoeducation interventions.

PE: Psychoeducation

PT: Psychotherapy

Table 6 Relapse of alcohol use and percentage of days abstinent at 6-month follow-up: intention to treat population using complete case and imputed data.

Outcome	Ketamine (n=)	Placebo (n=)	PT (n=)	PE (n=)	Ketamine + PT (n)	Ketamine + PE (n)	Placebo + PT (n)	Placebo + PE (n)	Ketamine vs placebo RR (95% CI)	Ketamine + PT vs Ketamine + PE RR (95% CI)	Ketamine + PT vs placebo +PE RR (95% CI)
Relapse; n (%) Timeline follow back											
									Ketamine vs placebo mean difference (95% CI)	Ketamine + PT vs Ketamine + PE mean difference (95% CI)	Ketamine + PT vs placebo +PE mean difference (95% CI)
Percentage days abstinent; mean (SD); median [IQR] Timeline follow back											

PE: Psychoeducation

PT: Psychotherapy

Table 7 Secondary outcomes at 3-month follow-up

Outcome	Ketamine (n=)	Placebo (n=)	PT (n=)	PE (n=)	Ketamine + PT (n)	Ketamine + PE (n)	Placebo + PT (n)	Placebo + PE (n)	Ketamine vs placebo mean difference (95% CI)
Number of continuous days abstinent ^{a,b} ; mean (SD), median [IQR]									
Percentage days abstinent ^{a,b} ; mean (SD); median [IQR]									

PE: Psychoeducation

PT: Psychotherapy

^aAbstinent means not using alcohol at all.

^bOutcomes measured using timeline follow-back.

Table 8 Secondary outcomes at 6-month follow-up

Outcome	Ketamine (n=)	Placebo (n=)	PT (n=)	PE (n=)	Ketamine + PT (n)	Ketamine + PE (n)	Placebo + PT (n)	Placebo + PE (n)	Ketamine vs placebo mean difference (95% CI)
Profile of Mood states; mean (SD), n									
Beck Depression Inventory; mean (SD)									
Hamilton Depression Scale; mean (SD), n									

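### The SAP's per-protocol rule demands three infusions of ketamine participants but none of placebo participants, and SAP 4.7 drops randomised participants whom the protocol keeps in the ITT analysis

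*SAP*

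**What the plan says.** **Per-protocol set.** SAP 4.5 gives the rule for one drug group: "For the participants who receive ketamine, a per protocol treatment will be defined as receiving three or more infusions". It then notes that no minimum was set for psychotherapy or psychoeducation, and continues: "Hence, all participants who receive placebo drug therapy will be considered as having been treated per protocol". The footnote to Table 5 in the SAP appendix repeats the position: "No definition of per protocol for placebo, psychotherapy, or psychoeducation interventions".

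The protocol makes no such distinction between arms. Section 13.3.2 describes an analysis "including only those participants deemed to have completed to a sufficient degree their allocated interventions, that is, a per protocol analysis", and section 8.1 schedules the control as "3 x weekly infusion of placebo (50ml Saline 0.9%) over 40 mins", the same number of infusions as ketamine.

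**ITT set.** SAP 4.7 says: "Participants found to be ineligible after randomisation will be excluded from all analyses". Protocol 13.3.2 says: "The primary analysis will be an intention-to-treat (ITT) complete case analysis including all randomised participants". Protocol 7.11.1 lists ineligibility, including ineligibility discovered in retrospect, as a reason to stop treatment. It still invites those participants to visits 9 and 10, and gives the ITT analysis as the reason.

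**The concern.** The missing therapy minimum does not explain the missing placebo minimum. Saline infusions are counted and scheduled exactly as ketamine infusions are, so one threshold can apply to both. That saline is inert is beside the point, because the issue is which patients are selected.

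People who miss infusions may differ from those who do not. Under protocol 7.9.1 a positive breathalyser ends an infusion visit, with the "patient invited to re-attend to complete the visit within the allocated visit window". Under 9.12, missing two consecutive infusions leads to withdrawal from treatment. Someone who resumes drinking early can therefore fall short of three infusions. That person leaves the ketamine set but stays in the placebo set.

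The affected comparisons are ketamine versus placebo, and ketamine plus psychotherapy versus placebo plus psychoeducation. Ketamine plus psychotherapy versus ketamine plus psychoeducation is not affected, since the rule is the same on both sides. A difference between the per-protocol and ITT results could come from the rule alone. A drug-specific rule also needs the drug allocation to apply it, which sits badly with the statistician's blinding in SAP 4.4 and 4.5.

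The second point concerns the primary analysis itself, whose population depends on which document is followed. SAP 4.7 does not say by when, by whom or under what blinding late ineligibility is judged. Nor does it limit the judgement to facts from before randomisation. One entry criterion (protocol 5.1, item 3) is current abstinence, which lies close to the outcome.

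**Working it through.** The plan states no figure for either point. The relapse rate and group size below come from protocol 13.2.1, whose interval reproduces. With 50% versus 25% and 24 per drug group, SE = √(0.25/24 + 0.1875/24) = 0.135, and 0.25 ± 1.645 × 0.135 gives 2.8% to 47.2%, against the stated 3% to 47%.

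**1. Per-protocol rule**

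Inputs:
- Relapse of 50% is the plan's placebo figure (protocol 13.2.1, SAP 4.6). It is applied here to completers.
- f, the share of those analysed who had fewer than three infusions, is assumed to be 10%, 25% or 40%.
- r, the relapse rate in that share, is assumed to be 90%, 70%, 50% or 30%.
- There is no drug effect, and f and r are the same in both drug groups.

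Under the SAP rule the ketamine set holds completers only, so its relapse rate is 0.50. The placebo set holds everyone, so its rate is (1 − f) × 0.50 + f × r. The expected relative risk (RR) is the first divided by the second.

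| f | r = 90% | r = 70% | r = 50% | r = 30% |
|---|---|---|---|---|
| 10% | 0.50/0.54 = 0.93 | 0.50/0.52 = 0.96 | 1.00 | 0.50/0.48 = 1.04 |
| 25% | 0.50/0.60 = 0.83 | 0.50/0.55 = 0.91 | 1.00 | 0.50/0.45 = 1.11 |
| 40% | 0.50/0.66 = 0.76 | 0.50/0.58 = 0.86 | 1.00 | 0.50/0.42 = 1.19 |

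Under the same assumptions, a common three-infusion rule gives 0.50/0.50 = 1.00 in every cell.

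Table 5 uses complete cases, so dropout matters. Assume 25% of those randomised are non-completers and 80% of them are lost, while 40% of completers are lost. Retained non-completers are 0.25 × 0.20 = 0.05 and retained completers are 0.75 × 0.60 = 0.45. Half are retained overall, as protocol 13.2.1 plans. Non-completers are then 0.05/0.50 = 10% of those analysed, and at r = 90% the RR is 0.93.

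A second parameterisation fixes relapse at 50% in the whole placebo group. Completers then relapse at (0.50 − f × r)/(1 − f), and the RR is that rate divided by 0.50. At r = 90% this gives:
- f = 10%: 0.456/0.50 = 0.91
- f = 25%: 0.367/0.50 = 0.73
- f = 40%: 0.233/0.50 = 0.47

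**2. ITT set**

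Assume 24/48 relapse in each drug group (RR 1.00) and that two participants are excluded from each group.
- Two relapsers leave ketamine and two non-relapsers leave placebo: (22/46)/(24/46) = 0.92.
- The reverse: (24/46)/(22/46) = 1.09.

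With the 24 per drug group left after planned dropout, starting from 12/24 each, the same removals give (10/22)/(12/22) = 0.83 and (12/22)/(10/22) = 1.20.

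**The case against.** **On the per-protocol rule.** The analysis is a sensitivity analysis, labelled exploratory and reported without p-values, and the Table 5 footnote shows readers the definition. It is also not the only check, since SAP 6.5 and Table 6 plan multiple imputation for both primary outcomes. All of this stands and limits the weight of the point. It does not make the rule sound: imputation deals with missing outcomes, not incomplete treatment, and a disclosed bias is still a bias.

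The sizes rest on assumptions. A positive breathalyser shows some drinking, whereas relapse needs five drinks (men) or four (women) on one occasion, and a missed visit can be rebooked. Nothing in the documents supports a 90% rate. The case that includes planned dropout gives 0.93, which is small against noise: for 12/24 versus 12/24, SE(log RR) = √(1/12) = 0.289 and the 95% CI is about 0.57 to 1.76. This also stands. The direction is plausible but not established.

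A common rule gives exactly 1.00 only if non-completion has the same causes in both groups. Protocol 9.11 withdraws participants from infusions for intolerable side effects, which may be commoner on ketamine. So a common rule can leave some bias, but that is no reason to add an avoidable asymmetry.

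**On the ITT set.** Eligibility is rechecked at visit 2 before randomisation, so exclusions may be few. Some late-ineligible participants will be withdrawn under 7.11.2 and lack six-month data under either document. The 0.92 to 1.09 range takes the extreme pattern of removals. Protocol 7.2 also says randomised participants enter the ITT analysis, but it speaks of compliance and dropout rather than ineligibility, so the conflict rests mainly on 13.3.2. These points limit the likely size. They do not reconcile the two definitions.

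**Conclusion.** Both points hold on the text.

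The per-protocol rule is one-sided and affects two of the three comparisons for both primary outcomes. For relapse, with no drug effect and completers relapsing at 50%, the expected RR runs from 0.76 to 1.19 over the assumed grid. It favours ketamine if non-completers relapse more than completers, is 1.00 if the rates are equal, and reverses if they relapse less. The primary analysis is not affected by this rule.

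The ITT population is defined in two incompatible ways, and this does reach the primary analysis. The direction is not fixed and the size depends on how many participants are excluded, which the documents do not give. Two per drug group out of 48 could move the RR to between 0.92 and 1.09.

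Confidence is high in the wording defects and lower in the sizes. Because the trial is exploratory, these should be fixed but do not by themselves undermine it.

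**What to change.** - **SAP 4.5 and the Table 5 footnote:** define the per-protocol set as participants who received all three of their allocated infusions, ketamine or saline, in both drug groups. State that the definition concerns infusions only, since no therapy minimum has been set.
- **SAP 4.7:** delete the sentence excluding participants found ineligible after randomisation, so that every randomised participant stays in the ITT population as protocol 13.3.2 requires. If the team wants to see the influence of late-ineligible participants, add a labelled sensitivity analysis. It should exclude only those who failed an entry criterion on data dated before randomisation, judged blind to allocation and outcome.

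The cost is SAP wording only, since administration of both ketamine and placebo infusions is already recorded (protocol 9.9 and 11.2). The placebo per-protocol group becomes somewhat smaller. A comparison of completers remains non-randomised, so the result is still supportive only.
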